9.3.3 Items of Investigation

9.3.3.1 Demographic data

For demographic evaluation, following background information of subjects shall be recorded:

- Subject signed date
- Subject study number
- Initial
- Gender
- Pregnancy
- Height
- Weight
- Year of birth(age)
- Smoking status

9.3.3.2 Medical history

The medical history to be collected prior to administration of this drug includes:

- Check hepatic or renal impairment
- Diagnosis
- Severity(Mild, Moderate, Severe)
- Date of diagnosis or date of surgery
- End date or continuation

9.3.3.3 Concomitant medication

Information on concomitant medication that is to be collected includes:

- Brand name
- generic name
- Route of medication
- Daily dose
- Unit
- Purpose of administration
- Indication
- Start date
- Date of discontinuation or continuation

9.3.3.4 Drug administration status

Information on the drug administration status includes:

- Dose
- Unit
- Start date
- Date of discontinuation or continuation

9.3.3.5 Information on the site

Information on the site includes:

- Hospital name
- Department
- Physician name

9.3.3.6 Result of laboratory tests(if applicable)

Information on the result of laboratory tests includes:

- Name of lab test
- Range of normal(Unit, Maximum and minimum data)
- Result of lab test before treatment
- Result of lab test after treatment

9.3.3.7 Overall evaluation

Information on the overall evaluation includes:

- Improved: If determined as there is any effect of maintaining or improving symptoms.
- Unchanged: If symptoms have not been changed compared with before administration, and not determined as there is any effect of maintaining symptoms.
- Aggravated: If symptoms are worse than before administration.
- Unassessible: If it cannot be determined due to insufficient information collected(Even though there are any objective indicators present, it is possible to belong to this grade.).

9.3.4 Outcomes of subjects Evaluation

9.3.4.1 Subject evaluation items

9.3.4.1.1 Number of cases who accepted the study

This number means the planned number of cases as specified in the contract concluded with the investigator(physician) prior to initiation of the study.

9.3.4.1.2 Number of cases subject who collected CRF

This number means the number of cases who signed the informed consent form to participate in the study as subject, and have record of taking Vahelva® Respimat® once at least.

9.3.4.1.3 Number of dropouts

These cases include those who signed the informed consent form to participate in this study as subject but did not meet any of the inclusion criteria, do not have any prescription record of Vahelva® Respimat®, have prescription record but have not been followed up by the physician following prescription and started administration prior to the signed date.

9.3.4.1.4 Number of cases subject to safety evaluation

These cases include those who signed the informed consent form to participate in this study as subject, took Vahelva® Respimat® once at least, and were completed follow up by the physician once or more.

9.3.4.1.5 Number of cases subject to effectiveness evaluation

These cases include those who signed the informed consent form to participate in this study as subject, visited as per the study schedule, took Vahelva® Respimat®, the cases included in safety evaluation, and were evaluated for the effectiveness including overall evaluation(if the case assessed as 'unassessable' will be excluded).

9.3.4.1.6 Subjects of special investigation

The patient who have signed on the data release consent form, subjects of special investigation(Pediatric or Adolescent(Younger than 18 years), Geriatric(Older than 65 years), Pregnant Women, renal impairment, hepatic impairment and other special population) among the patients who conducted investigation for safety assessment after the administration of Vahelva® Respimat® can be further investigation into cases collected from this study may be taken into account according to the outcome of retrospective analysis.

9.4 DATA SOURCES

This study will be carried out in the manner of successive survey that the investigator will be asked to successively write in the case report forms(CRFs) from the subject who was initially administered the drug following the study start date to the requested number of subjects without omission. Prior to initiation of the study, written contract shall be concluded, and this contract shall be concluded with the head of the site or the investigator with his/her consent.

9.5 STUDY SIZE

Sample size of 3,000 patients is based on the requirement of the local regulatory authority (MFDS). Since COPD is chronic disease it might be restrictive to collect data in just short-term (24±2weeks) period. The local regulatory authority(MFDS) recommends long-term(at least 52±2weeks) surveillance for maintaining approved indication. Thus all patients will be enrolled for long-term(52±2weeks) surveillance, basically.

Considering total surveillance size of 3,000 cases, at least 20%(600 cases) of total would be enrolled for long-term(52±2weeks) surveillance, even considering follow up loss in real world practice. Every institution will be contract for only one option of follow up period(short-term surveillance or long-term surveillance). It will be decided by feasibility check before to decide participation.

9.6 DATA MANAGEMENT

Patients' data will be gathered by eCRF. The data management procedures to ensure the quality of the data are described in detail in the data management plan (DMP) available in TMF. Data management and statistics will be outsourced to a qualified contract research organization (CRO).

9.7 DATA ANALYSIS

The safety evaluation will be performed on the “safety set” that will include all patients who have received treatment of Vahelva® Respimat® at least one time except those who are found to have no observation after enrolment, invalid registration, or invalid contract with the site. The effectiveness evaluation will be performed on the “effectiveness set”, a subset of the safety set, which will include all patients in the “safety set” except those who have no available effectiveness data and/or who do not suffer from COPD.

Medico-pharmaceutical assessment will be described with results of multiple regression analysis, 95% confidence intervals of every sub-analysis items of safety and effectiveness assessment.

Details are provided in the Statistical Analysis Plan (SAP).

9.7.1 Statistical design – model

In this NIS, all statistical analyses will be descriptive.

The level of statistical significance (p-value) and the precision (confidence interval) for the statistical analysis method used for exploratory purposes will be presented. Confirmatory hypothesis will not be conducted.

9.7.2 Demographic baseline data

Descriptive statistics will be performed that is data of demographics and medical health status of safety assessed cases. Average, standard deviation, min value, max value and median will be displayed for continuous data. The frequency will be conducted from categorical data.

Baseline characteristics (Demographics(all), co-morbidity, initial (pre-dose)FEV₁, (post bronchodilator predicted % of) FEV1, mMRC, co-medications, etc.) will be compared between the “long-term group” (patients who will be followed up for 52 weeks) and the “short-term group” (patients who will be followed up for 24 weeks) to put the data into perspective.

9.7.3 Analysis of Safety

Demographic and baseline characteristics will be summarized descriptively for the entire cohort of eligible patients.

Adverse events(AEs) from demographic data of safety assessment cases;

- Number of subjects and cases of AEs will be counted and incidence rate, 95% CI calculation.
- Calculate 95% confidence interval and rate of AEs. Analysis by one of methods of chi square test, fisher's exact test or logistic regression analysis methods in each item to find difference of AEs' rate or find factor that influence to safety profile.

Adverse Events (AEs) will be coded according to the latest version of Medical Dictionary for Drug Regulatory Affairs (MedDRA) coding system. The study database will not be locked until coding is complete.

Safety analyses will be based on all patients treated, i.e. all patients who received at least one dose of Vahelva® Respimat®. However, if data for patients who have been treated with Vahelva® Respimat® beyond the scope of approved label are collected, separate safety analyses will be performed. Safety analyses will be performed based on demographics and baseline characteristics.

Patients lost to follow up will be characterized compared to the remaining patients and reason and time point of loss to follow up will be evaluated.

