9.2 SETTING

As per regulations, enrolled patients will be followed up for 24 weeks or 52 weeks treatment period. There will be a visit window of ±2 weeks.

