9.3 VARIABLES

9.3.1 Safety

9.3.1.1 Outcome(s) of safety

All reported adverse events in patients who take at least once of Vahelva® Respimat® will be noted.

Outcomes pertaining to safety will be presented as incidence rates of adverse events and will include:

- Adverse events
- Unexpected adverse events
- Serious adverse events
- Adverse Drug Reactions
- Adverse events leading to discontinuation
- Adverse events by intensity, outcome of the events, causality

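### The adverse-event incidence and the factor tests pool patients followed for 24 and for 52 weeks, with no split, adjustment or time window in the protocol

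*Combined protocol and SAP*

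**What the plan says.** Safety is the primary objective (section 8.1). Section 9.3.1.1 states the outcome as follows: "Outcomes pertaining to safety will be presented as incidence rates of adverse events". It gives no period or denominator.

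Section 9.7.3 takes all patients with at least one dose. It plans: "Number of subjects and cases of AEs will be counted and incidence rate, 95% CI calculation". It then looks for influencing factors with one of "chi square test, fisher's exact test or logistic regression analysis methods in each item to find difference of AEs' rate", and adds: "Safety analyses will be performed based on demographics and baseline characteristics". The only other separate analysis it names is for use outside the label.

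Observation time differs by design. Section 9.2 says "enrolled patients will be followed up for 24 weeks or 52 weeks treatment period", and section 11.2 collects events from consent to the last visit. Section 9.5 sets the length by site: "Every institution will be contract for only one option of follow up period". On how the option is chosen, it says: "It will be decided by feasibility check before to decide participation". The long-term share is left open. The same section says "Thus all patients will be enrolled for long-term(52±2weeks) surveillance, basically", and then sets a floor of 20%, or 600 of 3,000 patients, allowing for follow-up loss.

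**The concern.** Chi-square, Fisher and logistic regression compare proportions. They take no account of how long each patient was watched unless a term for it is added, and the protocol names none. Long-term patients are observed for a little over twice as long (52/24 = 2.17).

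Two results suffer. First, the pooled incidence is a valid proportion for the mix of follow-up lengths that happens to be recruited, but it is not a risk over a known period, so it is hard to compare with other data. Second, follow-up length is set by a feasibility check at each site, not at random, and section 9.2.1 wants a balance of general hospitals and clinics. Age, severity or co-morbidity may therefore differ between the follow-up groups. Any factor that does can appear related to adverse events only because its carriers were observed longer.

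**Working it through.** **The plan's own figure.** 0.20 × 3,000 = 600, as section 9.5 states. The total of 3,000 is a regulatory requirement with no formula behind it.

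**Search for text that closes the gap.**
- Section 9.7 promises multiple regression and confidence intervals for sub-analysis items of safety, but names no follow-up term.
- Section 9.7.2 compares short-term and long-term groups, at baseline only.
- Section 9.7.4 distinguishes short-term and long-term cases, for effectiveness only.
- Sections 9.7.3 and 9.9.1 describe patients lost to follow-up. A patient who completes 24 weeks at a short-term site is not lost.
- Section 10 of the Annex 3 checklist ticks stratified analyses and confounding adjustment, but gives no method.
- The collection window in section 11.2 itself differs between the groups.

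None of these supplies a split, an adjustment or a time window for adverse events.

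**Size.** The documents give no adverse-event risk, loss rate or imbalance, so all of these inputs are assumptions:
- underlying risk of 10% at 24 weeks;
- cumulative hazard H(t) = −ln(0.90) × (t/24)^k, with k = 1 (constant) or k = 0.5 (front-loaded);
- loss either none, or exponential and reaching 30% by week 52, independent of events and equal in all groups.

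Observed risk by time T is the integral from 0 to T of h(t) × exp(−H(t)) × G(t), where h is the hazard and G the retention curve. With no loss and k = 1, the 52-week risk is 1 − 0.90^(52/24) = 0.2041. Pooled incidence at long-term share s is s × p52 + (1 − s) × p24, for example 0.2 × 0.2041 + 0.8 × 0.1000 = 0.1208.

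| Loss | k | p24 | p52 | Pooled, s = 20% | s = 50% | s = 100% |
|---|---|---|---|---|---|---|
| none | 1 | 0.1000 | 0.2041 | 0.1208 | 0.1520 | 0.2041 |
| none | 0.5 | 0.1000 | 0.1437 | 0.1087 | 0.1218 | 0.1437 |
| 30% | 1 | 0.0923 | 0.1728 | 0.1084 | 0.1326 | 0.1728 |
| 30% | 0.5 | 0.0949 | 0.1288 | 0.1017 | 0.1119 | 0.1288 |

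**Factor tests.** Take a factor with no effect on the hazard, 1,500 patients per level, a two-sided 5% two-proportion test, and no allowance for site clustering. With 30% against 10% long-term, k = 1 and no loss, the two proportions are 0.3 × 0.2041 + 0.7 × 0.1000 = 0.1312 and 0.1 × 0.2041 + 0.9 × 0.1000 = 0.1104. The difference is 0.0208. The standard error is about 0.0119, so the 5% threshold is 1.96 × 0.0119 = 0.0233. The rejection probability is about Φ((0.0208 − 0.0233)/0.0119) = 0.42.

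| Long-term share by level | k = 1, no loss | k = 1, loss | k = 0.5, no loss | k = 0.5, loss |
|---|---|---|---|---|
| 30% vs 10% | 0.417 (OR 1.22) | 0.294 (OR 1.18) | 0.120 (OR 1.09) | 0.094 (OR 1.08) |
| 25% vs 15% | 0.141 (OR 1.10) | 0.109 (OR 1.09) | 0.067 (OR 1.05) | 0.061 (OR 1.04) |
| 60% vs 40% | 0.355 | 0.255 | 0.113 | 0.091 |
| 95% vs 85% | 0.111 | 0.091 | 0.064 | 0.059 |

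Varying the 24-week risk from 2% to 30% moves the top-left figure between 0.127 and 0.783.

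**Does the remedy work?** The first two rows of the table give eight scenarios, each simulated with 4,000 studies (Monte Carlo standard error about 0.003). The pooled test rejects in 5.7% to 42.5%. The test limited to the first 24 weeks rejects in 4.7% to 5.4%. The Cochran-Mantel-Haenszel test stratified by follow-up group rejects in 4.4% to 5.7%.

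**The case against.** Section 9.7 defers detail to a SAP whose text was not supplied, and follow-up group could be one of the unnamed sub-analysis items there. That stands as a limit: the finding is that the protocol does not specify this, not that it will not be done.

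The 42% also stacks unfavourable assumptions: a threefold imbalance, constant hazard, no loss, equal halves, and all 3,000 patients in the safety set. With loss and a 600/2,400 split, 30% against 10% gives 22% (constant) or 8% (front-loaded). If nearly all sites are long-term, as one sentence of section 9.5 suggests, 95% against 85% gives only 6% to 11%. This is fair, and no document figure supports any particular imbalance. But the effect persists at intermediate mixes (9% to 36% at 60% against 40%), and sections 9.5 and 9.7.2 plan for two groups.

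All analyses are descriptive (section 9.7.1), and the baseline comparison in section 9.7.2 would show which factors track follow-up group. Both soften the consequence. Neither gives the incidence a period or adjusts the tests.

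Finally, crude 24- and 52-week proportions are still lowered by early loss. With 30% loss and constant hazard they read 9.2% and 17.3%, against underlying risks of 10.0% and 20.4%. The simulated return to nominal also assumes that loss is unrelated to events, whereas section 9.9.1 itself raises informative censoring. These are reasons to state how early loss is handled, not reasons to pool.

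**Conclusion.** The concern holds for the protocol text. Followed as written, section 9.7.3 gives an adverse-event incidence that depends on the site mix, and factor tests that can be confounded by observation time. With an assumed 10% risk at 24 weeks and no dropout, the range of long-term shares that section 9.5 allows moves the pooled incidence from 12.1% to 20.4% (constant hazard) or from 10.9% to 14.4% (front-loaded). False-positive rates for a null factor run from close to nominal (6%) to 42% in the eight scenarios, depending on hazard shape, loss and imbalance, all of them assumed. The problem shrinks towards ordinary dropout if almost every site is long-term. It affects how the primary safety result is read, not a confirmatory decision. It should be fixed; confidence is medium, because the SAP was not available and the real mix is unknown.

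**What to change.** In sections 9.3.1.1 and 9.7.3:

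1. Report adverse-event incidence with 95% CI over the first 24 weeks for all patients, and through week 52 for the long-term group.
2. Run the factor analyses on events in the first 24 weeks, or stratify by or adjust for follow-up group.
3. State the cut-off once, given the ±2-week visit window, and say how patients lost before it enter the denominator. Time-to-first-event or Cox methods are an optional addition.

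If the SAP already does this, align the protocol wording with it.

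The cost is wording and some programming. Visit dates (sections 9.2.3.2 to 9.2.3.4), drug start and stop dates (9.3.3.4) and mandatory onset dates (9.10.2.1) are already collected. Because section 9.7.6 allows incomplete event dates to be imputed, check events whose imputed onset falls near the cut-off.

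Limiting the factor tests to 24 weeks loses events. Under the assumptions above it keeps 83% (0.1000/0.1208) to 93% (0.0949/0.1017) of patients with an event at 20% long-term, and 49% (0.1000/0.2041) to 74% (0.0949/0.1288) at 100% long-term. Stratifying or adjusting keeps all events.

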9.7.4 Analysis of Effectiveness

Effectiveness assessment of short-term and long-term cases will be analysis. Effectiveness rate and 95% confidence interval of demographic data will be calculated. One of methods of chi square test, fisher's exact test or logistic regression analysis methods will be use appropriately.

9.7.4.1 Main outcome analyses

A descriptive analysis of effectiveness outcomes is planned. For patients treated with Vahelva® Respimat®, the change of Post Bronchodilator Predicted % FEV1 from baseline and last follow-up visit will be calculated. Effectiveness analysis will be performed based on demographic characteristics and baseline characteristics.

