9.2.1 Study sites

A total of 3,000 patients will be enrolled at approximately 50 sites by as many as 50 or more NIS physicians. To minimize the selection bias at the site level, the goal is to have participating centers reflect a balance between general hospitals and clinics for surveillance. The treating physicians will mainly be Respiratory Internists. To minimize the selection bias, consecutive patients from each site who meet inclusion criteria will be enrolled in this study.

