9.3.2 Effectiveness

9.3.2.1 Outcome(s) of effectiveness

9.3.2.1.1 Main outcome

- Change from baseline in (Post Bronchodilator Predicted %) FEV₁ after 24 weeks and/or 52 weeks of treatment

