9.3.2.1.2 Other outcomes

- Change from baseline in Pre-dose FEV₁ after 24 weeks and/or 52 weeks of treatment
- Change from baseline in mMRC score after 24 weeks and/or 52 weeks of treatment
- Overall evaluation(Improved, unchanged, aggravated or unassessable) by investigator based on overall clinical assessment including change from baseline in effectiveness assessment((Post bronchodilator predicted % of) FEV1, (pre-dose) FEV₁, mMRC scale) after 24 weeks or 52 weeks of treatment. 'Improved' is assessed as "Effective", 'Unchanged, Aggravated' are assessed as "Invalid".

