9.7.4.2 Other outcome analyses

A descriptive analysis of effectiveness outcome is planned. For patient treated with Vahelva Respimat, the change of (pre-dose) FEV₁ from baseline and last follow up visit will be calculated. Effectiveness analysis will be performed based on demographic characteristics and baseline characteristics.

A descriptive analysis of effectiveness outcome is planned. For mMRC, descriptive statistics will be calculated. Effectiveness analysis will be performed based on demographic characteristics and baseline characteristics.

A descriptive analysis of effectiveness outcomes is planned. For overall evaluation, descriptive statistics will be calculated for assessed one of the items(improved, unchanged, worsen or not applicable) by investigator with medical opinion of each individual component and the changes from scores before first administration. Effectiveness analysis will be performed based on demographic characteristics and baseline characteristics.

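### FEV1 change is analysed to the last follow-up visit, which is week 24 or week 52 depending on the site's contract; change should be reported by scheduled week and follow-up group

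*Combined protocol and SAP*

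**What the plan says.** **The analysis rule.** For the main effectiveness outcome, 9.7.4.1 states that "the change of Post Bronchodilator Predicted % FEV1 from baseline and last follow-up visit will be calculated". For pre-dose FEV1, 9.7.4.2 likewise has the change "from baseline and last follow up visit will be calculated". For dyspnoea it says only "For mMRC, descriptive statistics will be calculated". None of the three names a week or a follow-up group.

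**The outcome definitions.** Section 9.3.2.1.1 defines the main outcome as change "after 24 weeks and/or 52 weeks of treatment", and 9.3.2.1.2 has "Change from baseline in mMRC score after 24 weeks and/or 52 weeks of treatment". Both weeks are named, but the choice between them is left open.

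**Follow-up length.** Section 9.2 says that "enrolled patients will be followed up for 24 weeks or 52 weeks treatment period". Section 9.5 adds "Every institution will be contract for only one option of follow up period", with the option settled by a feasibility check. The same section says that in principle all patients are enrolled for 52 weeks, and then sets a minimum of 20% (600 of 3,000) for long-term surveillance.

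**The two groups.** Section 9.7.4 says that the effectiveness of short-term and long-term cases will be analysed, without saying separately or at which week. Section 9.7.2 defines the two groups, but only to compare their baseline characteristics.

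**Who is analysed.** Section 9.3.4.1.5 limits the effectiveness cases to patients who attended according to the visit schedule. Section 9.7 removes from the safety set only patients with no effectiveness data or without COPD. Section 9.7 also refers details to an SAP.

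**The concern.** The last scheduled visit falls at week 24 at some sites and at week 52 at others. Taken literally, a single mean change to the last visit is then an average over two time points, weighted by how many sites chose each contract. Such a mean may be neither a 24-week nor a 52-week result, although 9.5 reports that the authority recommends surveillance of at least 52 weeks.

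The same can happen inside the long-term group. A long-term patient who never reaches Visit 3 has a last visit at week 24, and the two definitions of the effectiveness set give different answers on whether that patient counts. Two analysts working from this protocol could therefore report different main effectiveness results from the same data.

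What is at stake is how the FEV1 and mMRC results can be read. Effectiveness is the secondary objective (8.2) and all analyses are descriptive (9.7.1), so no error rate, power or sample size is affected.

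**Working it through.** **Inputs from the protocol.** Total size 3,000; long-term minimum 20%, stated as 600 (both 9.5); follow-up of 24 or 52 weeks (9.2); about 50 sites (9.2.1). The plan's own figure reproduces: 0.20 × 3,000 = 600.

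**1. Weights if all last-visit values are pooled.** Let m be the long-term share and assume complete data. Week-24 values = 3,000(1 − m); week-52 values = 3,000m; nominal mean time = 24(1 − m) + 52m.

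| m | week-24 values | week-52 values | week-24 weight | nominal mean time |
|---|---|---|---|---|
| 0.2 (stated minimum) | 2,400 | 600 | 80% | 29.6 weeks |
| 0.5 (assumed) | 1,500 | 1,500 | 50% | 38.0 weeks |
| 1.0 (all long-term) | 0 | 3,000 | 0% | 52.0 weeks |

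**2. Long-term group alone.** Let d be the share of analysed long-term patients with no Visit 3 who contribute a Visit 2 value. Nominal mean time = 24d + 52(1 − d): 49.2 weeks at d = 0.1, 46.4 at 0.2 and 40.8 at 0.4. These shares are assumptions; the documents give no loss rate.

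**3. Effect on the mean.** If the true mean changes are c24 and c52, and are the same in both groups, the pooled mean is (1 − m)c24 + m·c52. It differs from the 52-week mean by (1 − m)(c24 − c52), which is 80% of the difference between the weeks at m = 0.2. With assumed changes of 4 and 2 percentage points the pooled mean is 0.8 × 4 + 0.2 × 2 = 3.6; with 2 and 4 it is 2.4; with equal changes pooling does no harm. The documents give no expected change or SD, so the real size cannot be computed.

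**4. Time and site.** Because a site has one follow-up length, setting week 24 in the short-term group against week 52 in the long-term group mixes time with site. With equal site sizes (assumed), 3,000/50 = 60 patients per site, so the 600 minimum is 600/60 = 10 sites against 40. Long-term patients also have Visit 2 (4.1), so a week-24 comparison between groups has no time difference, although the sites still differ.

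**5. Precision of a separate week-52 result.** The 95% CI half-width in SD units with independent patients is 1.96/√n: 0.080 at n = 600 and 0.040 at n = 2,400. With 10 sites of 60 and an assumed ICC of 0.01 to 0.05, the design effect is 1 + 59 × ICC = 1.59 to 3.95. With only 10 sites a t multiplier on 9 df (2.262) is appropriate: 2.262/√600 = 0.0923; × √1.59 = 0.12; × √3.95 = 0.18.

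**The case against.** The strongest reply is that a by-group analysis is probably intended. Section 9.7.4 names short-term and long-term cases directly above the rule, 9.3.2.1 names both weeks, 9.7.2 defines the groups, and the flow chart records study completion at both follow-up visits. On that reading the last visit is shorthand for each group's end visit, and the SAP to which 9.7 refers may say so. This stands in part: no sentence prescribes a pooled mean, and the text available for this review includes no SAP sections. But the rule that is stated, applied literally, does combine the weeks, and nothing in the protocol says that it is applied within group.

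Three stronger readings are tempting, and the documents do not support them.

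- A reader might infer that a difference between the groups reflects site type, since 9.2.1 aims to have "participating centers reflect a balance between general hospitals and clinics for surveillance". No section links follow-up length to hospital or clinic, the feasibility criterion is not given, and 9.10 says that all selected sites have their own hospital review board.
- A reader might infer that week and site are confounded in every comparison between the groups. That is true only of week 24 against week 52; both groups have a week-24 visit.
- A reader might infer that a Visit 2 value replaces any missing week-52 value, because follow-up FEV1 is collected only where applicable and 9.7.6 uses all available data. But the rule refers to the last visit, not the last available value, and 9.7.6 is not a carry-forward rule. A patient who attends Visit 3 without spirometry simply has no value at the last visit. Only the patient with no Visit 3 is truly ambiguous.

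It is also fair to note that 9.7.3 and 9.9.1 already plan to describe patients lost to follow-up, with the reason and time point. That helps interpretation but does not fix the week at which change is reported.

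**Conclusion.** The point holds as a cheap improvement to a secondary, descriptive analysis. The last-visit rule can combine week-24 and week-52 values, and the mMRC analysis has no stated time point. At the 20% minimum, with pooling and complete data, 80% of values would come from week 24. That weight falls to zero if all sites are long-term and no long-term patient leaves before Visit 3. It shows how far the label and the content of the mean could differ, not how large a bias is.

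The conflict between 9.3.4.1.5 and 9.7 over a long-term patient without Visit 3 remains whatever the long-term share. If the SAP already names weeks and groups, only the protocol wording needs aligning.

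**What to change.** In 9.7.4.1 and 9.7.4.2:

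- Report observed change in both FEV1 measures and in mMRC at week 24 in the short-term group, and at weeks 24 and 52 in the long-term group. Give the numbers observed and missing each time, with the 95% CIs that 9.7 already promises.
- Keep change to the last visit as a supportive summary, labelled as such.
- Read week 24 against week 52 within long-term patients who have both values, not between groups.

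Reconcile 9.3.4.1.5 with 9.7 by stating whether a long-term patient without Visit 3 is in the effectiveness set. If such patients are excluded, label the result as one in completers. As a minor matter, align the Visit 3 list in 9.2.3.4 with the flow chart, which schedules the overall evaluation there while the list omits it.

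The cost is wording only, with no new procedures or data. The price is several estimates instead of one, with week 52 resting on fewer patients: at n = 600, a half-width of 0.08 SD if patients are independent, or about 0.12 to 0.18 SD under the clustering assumptions above.
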